### 5.10. Concomitant Treatment(s)

Medication entries should provide the correctly spelled drug or therapy name and the dose, units, frequency, route of administration, start and stop date, and reason for use. The use of any concomitant medication must relate to the subject's medical history or to an AE, except for vitamins/nutritional supplements and routine immunizations.

### Cohort 1

Subjects will abstain from all concomitant treatments, except for the treatment of AEs. Limited use of nonprescription medications that are not believed to affect subject safety or the overall results of the study may be permitted on a case-by-case basis following approval by the sponsor.

Treatments taken within 28 days before the first application of investigational product will be documented as a prior treatment. Treatments taken after the first application of investigational product will be documented as concomitant treatments.

## Cohort 2

All treatments (including medications and non-medication therapies) used for the treatment of AD and all other medications (including over-the-counter drugs, vitamins, and antacids) used within 28 days prior to Screening will be recorded at the Screening visit. Any changes in concomitant medications or dosage will be recorded on Day 1 and at each subsequent visit. Treatments taken after the first application of investigational product will be documented as concomitant treatments

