- Review and record concomitant medications;
- Assess the skin irritation response of the patch sites by a blinded observer approximately 24 hours after removal of the patches;

- Assess symptoms by spontaneous reporting of AEs and by asking the subjects to respond to a nonleading question such as "How do you feel?" If AEs/SAEs occur at a patch site, the patch site location must be recorded;
- Conduct physical examination;
- Discharge from CRU confinement.

If a subject has any clinically significant, study-related abnormalities at the conclusion of a scheduled inpatient portion of the study, the Pfizer medical monitor (or designated representative) should be notified and the subject may be asked to remain in the CRU until such abnormalities are deemed not clinically significant, or it is safe for outpatient follow-up. If the subject is unable or unwilling to remain in the CRU and/or when outpatient follow-up is deemed appropriate, the Pfizer medical monitor (or designated representative) should be so notified, and the investigator should make every effort to arrange follow-up evaluations at appropriate intervals to document the course of the abnormalities.

#### 6.2.2. Cohort 2

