#### 7.1.6. Skin Irritation Assessment (Cohort 1)

Skin irritation assessment of the patch sites will be conducted on Day 3 (approximately 30 minutes after removal of the patches) and Day 4 (approximately 24 hours after removal of the patches) by a blinded observer who is a dermatologist. The following grade and score will be used to evaluate the response observed at the time of examination 20,21,22:

Table 4.	Skin I	rritation	Assessment	Grades and	Scores

Definition	Grade	Score
No reaction	=	0
Mild erythema	±	0.5
Erythema	+	1
Erythema + edema, papula	++	2
Erythema + edema + papula + small water blister	+++	3
Large water blister	++++	4

Expected reactions in the patch area (ie, irritation reactions outlined in Table 4 above) will not be recorded as AEs during the study. Unexpected reactions (eg, rash, hives) will be recorded as AEs.

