# 8.1.4.2. Recording Non-serious AEs and SAEs on the CRF

During the active collection period, both non-serious AEs and SAEs are recorded on the CRF.

Follow-up by the investigator may be required until the event or its sequelae resolve or stabilize at a level acceptable to the investigator, and Pfizer concurs with that assessment.

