# 8.4. Special Situations

# 8.4.1. Protocol-Specified Serious Adverse Events

There are no protocol-specified SAEs in this study. All SAEs will be reported to Pfizer Safety by the investigator as described in previous sections, and will be handled as SAEs in the safety database.

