#### CCI

## 9.5. Safety Analysis

The safety analysis will be conducted for Cohort 1 and Cohort 2, separately.

The safety analysis population is defined as all subjects who receive at least one dose of study medication.

AEs, ECGs, BP, PR and safety laboratory data will be reviewed and summarized on an ongoing basis during the study to evaluate the safety of subjects. Any clinical laboratory, ECG, BP, PR abnormalities of potential clinical concern will be described. Safety data will be presented in tabular and/or graphical format and summarized descriptively, where appropriate.

Physical examination information collected during the course of the study will be considered source data and will not be required to be reported, unless otherwise noted. However, any untoward findings identified on physical examinations conducted during the active collection period will be captured as AEs, if those findings meet the definition of an AE. Data collected at screening that are used for inclusion/exclusion criteria, such as laboratory data, ECGs, and vital signs, will be considered source data, and will not be required to be reported, unless otherwise noted. Demographic data collected at screening will be reported.

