#### 6.2. Secondary Endpoints

#### **6.2.1.** Adverse Events

AEs are the sencondary endpoint for Cohort 1. The analysis of AEs will be based on the safety analysis population. Descriptive summaries and listing of the AE/SAE data will be provided. In addition, AEs occurred in the application area will be summarized by treatment separately. AEs will be reported in accordance with the Pfizer data standards.

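### Protocol 7.1.6 keeps every Table 4 patch reaction out of AE recording, with no exception for a non-serious reaction that is treated or leads to early patch removal or withdrawal

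*Protocol*

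**What the plan says.** Protocol 7.1.6 has a blinded dermatologist score each patch site on Day 3 and Day 4 using Table 4, which runs from 0 (no reaction) to 4 (large blister). On AE recording it says: "Expected reactions in the patch area (ie, irritation reactions outlined in Table 4 above) will not be recorded as AEs during the study". Only unexpected reactions, with rash and hives as examples, are recorded as AEs.

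AEs are the Cohort 1 secondary endpoint (Protocol 2). For that cohort, SAP 6.2.1 adds that "AEs occurred in the application area will be summarized by treatment separately".

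On medication, Protocol 5.10 has a rule for the whole study, "The use of any concomitant medication must relate to the subject's medical history or to an AE" (vitamins, supplements and routine immunizations aside), and one for Cohort 1: "Subjects will abstain from all concomitant treatments, except for the treatment of AEs". It also lets Cohort 1 subjects use limited nonprescription medication case by case with sponsor approval.

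The general safety sections are broader. Protocol 8.1.4.2 says "During the active collection period, both non-serious AEs and SAEs are recorded on the CRF". Protocol 8.4.1 says "All SAEs will be reported to Pfizer Safety by the investigator as described in previous sections". The Cohort 1 procedures in Protocol 6.2.1 foresee local events: "If AEs/SAEs occur at a patch site, the patch site location must be recorded".

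**The concern.** It is reasonable to keep routine scored irritation out of the AE tables, because it is the primary endpoint and would otherwise be counted twice. The difficulty is that the exemption depends only on what the reaction looks like and not on what follows from it. A blister that is treated, or that makes the site take the patch off early or withdraw the subject, is exempt on the same terms as faint redness.

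At stake is the completeness of the secondary safety summary. The AE record is also where causality (Protocol 8.1.5), intensity (8.3) and follow-up to resolution (8.1.4.2) are documented. An irritation score describes morphology and carries none of these. In addition, treating a reaction that is not an AE fits poorly with the medication rule in Protocol 5.10.

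**Working it through.** The plan states no figure on this point, so the check is mainly a comparison of rules, followed by a small illustration.

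**Step 1. Is there an exception to 7.1.6?** The places where one might be found are:

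- *Protocol 7.1.6* itself attaches no condition. The only route to an AE is a reaction of a different type.
- *Protocol 8.2.2* makes abnormal objective test findings AEs when they need intervention, change dosing, lead to discontinuation or to significant added treatment, or are judged to be AEs by the investigator or sponsor. These triggers are close to the missing exception. The section does not mention patch reactions or 7.1.6, and it is arguable whether a visual skin grade is an objective test finding.
- *Protocol 9.5* says that "any untoward findings identified on physical examinations conducted during the active collection period will be captured as AEs", provided that they meet the AE definition. A physical examination is scheduled on Day 4 or at early termination, so this could catch a reaction present then. It does not say that it overrides 7.1.6.
- *Protocol 8.1.3* separates withdrawal due to AEs from other withdrawal, which presupposes that the event counts as an AE.
- *Protocol 6.4* asks for the patch sites to be scored at early withdrawal and gives no AE rule for what is found. Early patch removal is not addressed.

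No stated exception exists. The general rules pull towards recording, and the specific rule points away from it.

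**Step 2. Does the treatment rule fit?** Under Protocol 5.10 a medication needs a link to medical history or to an AE. A new Table 4 reaction is not medical history and, under 7.1.6, is not recorded as an AE. Sponsor-approved nonprescription use gives permission in some cases but does not supply that link.

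**Step 3. Where would the reaction still appear?** If it is present at a scoring visit, it appears by product in the index (SAP 6.1.1), in the score frequencies and in the individual listing (SAP 6.3.1). Its treatment appears in the medication listing. The matching medication summary is for Cohort 1 as a whole (SAP 6.5.4), so it cannot separate crisaborole from vehicle when every subject wears both patches. A discontinuation is counted (SAP 6.5.2), and treatment duration is summarized by product (SAP 6.5.3).

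**Step 4. Size, for illustration.** Assume 20 evaluable subjects (Protocol 3.1), one such reaction to one product, and all other scores 0.

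- Application-area AE summary with 7.1.6 followed: 0/20 = 0%. With the reaction recorded: 1/20 = 5%.
- Skin irritation index = sum of maximum scores / number evaluable × 100 (Protocol 9.5.2):

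| Score of the one reaction | Index | Table 5 category |
|---|---|---|
| 2 | 2/20 × 100 = 10 | Acceptable |
| 3 | 3/20 × 100 = 15 | Acceptable |
| 4 | 4/20 × 100 = 20 | Improvable |

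The index is the same whether or not the reaction is also an AE. The documents give no rate for such reactions. The earlier 21-day patch study found only very minimal irritation (Protocol 1.3.3.2).

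**The case against.** The strongest reply is that Protocol 8.2.2 already covers the case. Its triggers nearly match the exception asked for, patch scoring is a scheduled safety assessment under Protocol 7.1, and the clause on investigator or sponsor judgment is wide. A site could reasonably record a treated blister on that basis, and the medication rule in 5.10 gives it a further reason to do so. This stands in part: one cannot say that such an event will certainly be missing from the AE summary. What remains is that the specific and unconditional sentence says the opposite and nothing settles which governs.

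A second reply is that little is lost, because the scores, index, listings, exposure and disposition outputs show much of the event and no hypothesis is tested (SAP 5.1). This also stands, and it limits the weight of the point. It does not replace the causality, severity and follow-up record.

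A third reply is that the remedy has a cost. In Cohort 1 everyone at the site except the observer is unblinded (Protocol 5.2), so staff who know the product could decide which scored reactions become AEs. That is true, although other Cohort 1 AEs already carry this limit.

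A reader might infer two stronger things. One is that a serious patch reaction would go unreported. The documents do not support this: Section 8 requires all SAEs to be reported, and the Cohort 1 procedures expect SAEs at patch sites, so there the matter is only unreconciled wording. The other is that 5.10 forbids treating a reaction. It does not: it allows treatment of AEs and, with approval, limited nonprescription use.

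**Conclusion.** The point holds as a minor one. Protocol 7.1.6 gives an unconditional instruction that conflicts with general rules elsewhere. If it is followed, a non-serious Table 4 reaction that is treated, or that ends patch wear or participation, is left out of the SAP 6.2.1 application-area summary and has no AE record. For a single case in 20 subjects the difference is 0% against 5%. The primary index and its category do not change, and the event is unlikely.

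It would go too far to say that the reaction is concealed, since it is scored by product and listed. That does assume it is present when the site is scored. Scheduled scoring ends on Day 4 while AE follow-up runs to Day 29 (+7 days), so a reaction arising after discharge would have no scheduled score.

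The conclusion also rests on sites giving the specific rule precedence. It assumes that neither the skin irritation manual cited in Protocol 5.7.1 nor the sponsor data standards cited in SAP 3.5.1 and 6.2.1 supplies the missing exception. Neither source is among the documents, so this cannot be ruled out.

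**What to change.** Keep the exemption for routine scored irritation and add to Protocol 7.1.6: *A Table 4 reaction is also recorded as an AE if it requires treatment or leads to early patch removal or withdrawal (consistent with Section 8.2.2); Section 8 prevails for any reaction meeting an SAE criterion.* A treated reaction then satisfies Protocol 5.10 without further change, and the patch location is already collected. Footnote the SAP 6.2.1 table to say that these events appear in both the index and the AE table.

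The cost is one protocol sentence, matching CRF guidance and one SAP footnote. The index calculation is untouched. There are two downsides. A few events are shown twice, which the footnote discloses. And, as for other Cohort 1 AEs, the decision to treat or to remove a patch may be made by unblinded staff.

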#### 7.2. Pharmacokinetics

# 7.2.1. Plasma for Analysis of crisaborole and main metabolites (Cohort 2)

During all study periods, blood samples (2 mL) to provide a minimum of 0.4 mL plasma for PK analysis will be collected into appropriately labeled tubes containing dipotassium ethylenediaminetetraacetic acid (K2EDTA) at times specified in the SCHEDULE OF ACTIVITIES section of the protocol.

The actual times may change, but the number of samples will remain the same. All efforts will be made to obtain the PK samples at the exact nominal time relative to dosing. However, samples obtained within 10% of the nominal time (eg, within 6 minutes of a 60-minute sample) from dosing will not be captured as a protocol deviation, as long as the exact time of the sample collection is noted on the source document and data collection tool (eg, CRF).

Samples will be analyzed using a validated analytical method in compliance with Pfizer standard operating procedures (SOPs).

The PK samples must be processed and shipped as indicated in the instructions provided to the investigator site to maintain sample integrity. Any deviations from the PK sample handling procedure (eg, sample collection and processing steps, interim storage or shipping conditions), including any actions taken, must be documented and reported to the sponsor. On a case-by-case basis, the sponsor may make a determination as to whether sample integrity has been compromised. Any deviation from the specified sample handling procedure resulting in compromised sample integrity will be considered a protocol deviation.

As part of understanding the PK of the investigational product, samples may be used for metabolite identification and/or evaluation of the bioanalytical method, as well as for other internal exploratory purposes. These data will not be included in the clinical study report (CSR).

# 7.4. Blood Volume

The total blood sampling volume for individual subjects in this study is approximately 20 mL for Cohort 1 or 53 mL for Cohort 2, respectively. The actual collection times of blood sampling may change. Additional blood samples may be taken for safety assessments at times specified by Pfizer, provided the total volume taken during the study does not exceed 550 mL during any period of 60 consecutive days.

#### 8. ADVERSE EVENT REPORTING

# 8.1. Requirements

The table below summarizes the requirements for recording safety events on the CRF and for reporting safety events on the Clinical Trial (CT) Serious Adverse Event (SAE) Report Form to Pfizer Safety. These requirements are delineated for 3 types of events: (1) SAEs; (2) non-serious adverse events (AEs); and (3) exposure to the investigational product under study during pregnancy or breastfeeding, and occupational exposure.

Safety Event	Recorded on the CRF	Reported on the CT SAE Report Form to Pfizer Safety Within 24 Hours of Awareness
SAE	All	All
Non-serious AE	All	None
Exposure to the investigational product under study during pregnancy or breastfeeding, and occupational exposure	All (regardless of whether associated with an AE), except occupational exposure	Exposure during pregnancy, exposure via breastfeeding, occupational exposure (regardless of whether associated with an AE)
Abbreviations: CRF=case report forn	r; CT=clinical trial; SAE=serious ad	,

All observed or volunteered events regardless of treatment group or suspected causal relationship to the investigational product(s) will be reported as described in the following paragraphs.

Events listed in the table above that require reporting to Pfizer Safety on the CT SAE Report Form within 24 hours of awareness of the event by the investigator are to be reported regardless of whether the event is determined by the investigator to be related to an investigational product under study. In particular, if the SAE is fatal or life-threatening, notification to Pfizer Safety must be made immediately, irrespective of the extent of available event information. This time frame also applies to additional new (follow-up) information on previously forwarded reports. In the rare situation that the investigator does not become immediately aware of the occurrence of an event, the investigator must report the event within 24 hours after learning of it and document the time of his/her first awareness of the event.

For each event, the investigator must pursue and obtain adequate information both to determine the outcome and to assess whether it meets the criteria for classification as an SAE (see the Serious Adverse Events section below). In addition, the investigator may be requested by Pfizer Safety to obtain specific follow-up information in an expedited fashion. This information is more detailed than that recorded on the CRF. In general, this will include a description of the event in sufficient detail to allow for a complete medical assessment of

the case and independent determination of possible causality. Any information relevant to the event, such as concomitant medications and illnesses, must be provided. In the case of a subject death, a summary of available autopsy findings must be submitted as soon as possible to Pfizer Safety. Any pertinent additional information must be reported on the CT SAE Report Form; additional source documents (eg, medical records, CRF, laboratory data) are to be sent to Pfizer Safety **ONLY** upon request.

As part of ongoing safety reviews conducted by the sponsor, any non-serious AE that is determined by the sponsor to be serious will be reported by the sponsor as an SAE. To assist in the determination of case seriousness, further information may be requested from the investigator to provide clarity and understanding of the event in the context of the clinical study.

# 8.1.1. Additional Details on Recording Adverse Events on the CRF

All events detailed in the table above will be recorded on the AE page(s) of the CRF. It should be noted that the CT SAE Report Form for reporting of SAE information is not the same as the AE page of the CRF. When the same data are collected, the forms must be completed in a consistent manner. AEs should be recorded using concise medical terminology and the same AE term should be used on both the CRF and the CT SAE Report Form for reporting of SAE information.

# **8.1.2.** Eliciting Adverse Event Information

The investigator is to record on the CRF all directly observed AEs and all AEs spontaneously reported by the study subject. In addition, each study subject will be questioned about the occurrence of AEs in a non-leading manner.

# 8.1.3. Withdrawal From the Study Due to Adverse Events (see also the Subject Withdrawal section)

Withdrawal due to AEs should be distinguished from withdrawal due to other causes, according to the definition of AE noted below, and recorded on the CRF.

When a subject withdraws from the study because of an SAE, the SAE must be recorded on the CRF and reported, as appropriate, on the CT SAE Report Form, in accordance with the Requirements section above.

# 8.1.4. Time Period for Collecting AE/SAE Information

The time period for actively eliciting and collecting AEs and SAEs ("active collection period") for each subject begins from the time the subject provides informed consent, which is obtained before the subject's participation in the study (ie, before undergoing any study-related procedure and/or receiving investigational product), through and including a minimum of 28 calendar days after the last administration of the investigational product.

For subjects who are screen failures, the active collection period ends when screen failure status is determined

# 8.1.4.1. Reporting SAEs to Pfizer Safety

All SAEs occurring in a subject during the active collection period are reported to Pfizer Safety on the CT SAE Report Form.

SAEs occurring in a subject after the active collection period has ended are reported to Pfizer Safety if the investigator becomes aware of them; at a minimum, all SAEs that the investigator believes have at least a reasonable possibility of being related to investigational product must be reported to Pfizer Safety.

Follow up by the investigator continues throughout and after the active collection period and until the event or its sequelae resolve or stabilize at a level acceptable to the investigator, and Pfizer concurs with that assessment.

# 8.1.4.2. Recording Non-serious AEs and SAEs on the CRF

During the active collection period, both non-serious AEs and SAEs are recorded on the CRF.

Follow-up by the investigator may be required until the event or its sequelae resolve or stabilize at a level acceptable to the investigator, and Pfizer concurs with that assessment.

# 8.1.5. Causality Assessment

The investigator's assessment of causality must be provided for all AEs (serious and non-serious); the investigator must record the causal relationship on the CRF, and report such an assessment in accordance with the SAE reporting requirements, if applicable. An investigator's causality assessment is the determination of whether there exists a reasonable possibility that the investigational product caused or contributed to an AE; generally the facts (evidence) or arguments to suggest a causal relationship should be provided. If the investigator does not know whether or not the investigational product caused the event, then the event will be handled as "related to investigational product" for reporting purposes, as defined by the sponsor. If the investigator's causality assessment is "unknown but not related" to investigational product, this should be clearly documented on study records.

In addition, if the investigator determines that an SAE is associated with study procedures, the investigator must record this causal relationship in the source documents and CRF, and report such an assessment in the dedicated section of the CT SAE Report Form and in accordance with the SAE reporting requirements.

